#### **6.4.6. Discontinuation of Investigational Product**

Subjects who temporarily or permanently discontinue IP, should remain in the study and continue to be followed at all scheduled visits, for the duration of the study. Subjects with the temporary discontinuation of IP should resume its administration when deemed appropriate by the investigator and, if necessary, with consultation of the Sponsor. Only subjects who have permanently discontinued IP are classified as Off Drug In Study (ODIS) subjects. ODIS subjects are not expected to, or planned to resume the administration of IP. ODIS subjects should remain in contact with the investigator, either by attending study visits or via phone visit, throughout the remainder of the study. The sole exception to continuing some level of contact with the investigator is if a subject fully withdraws consent, as described in [Section 6.5](#). Temporary or permanent discontinuation of IP and/or resumption of IP after a temporary discontinuation, must be registered in the IRT.

For all ODIS and Withdrawn Consent subjects the study site must discuss the case with a study team member, ie, retention hotline or delegate to discuss the subject status and ensure continued follow-up in the study. The study management team will provide to the study site, an EDC retention hotline and a study retention toolkit, to define potential levels of the subject's continued participation in the study, even if the subject is no longer taking IP (ie, an ODIS subject). Every effort must be made to retain subjects in the study, even if they are no longer taking IP.

### **6.5. Subject Withdrawal**

#### **6.5.1. Withdrawal of Consent**

Subjects who withdraw consent are defined as those subjects who refuse any further contact with the investigator or persons authorized by the subject, previously, to receive the subject's study information. Subjects should notify the investigator of the decision to withdraw consent from future follow-up in writing, whenever possible. The reason for withdrawal of

consent should be explained in detail in the medical records by the investigator, as to whether the withdrawal is from further treatment with study drug only or also from study procedures and/or post treatment study follow-up, and entered on the appropriate CRF page. The investigator should document thoroughly, the efforts by the site to retain the subject by offering the subject the opportunity to remain in the study as an ODIS subject with complete study visits or lesser degrees of follow up (ie, phone contact). In the event that vital status (whether the subject is alive or dead) is being measured, publicly available information should be used to determine vital status only as appropriately directed in accordance with local law.

Subjects may withdraw from the study at any time at their own request, or they may be withdrawn at any time at the discretion of the investigator or sponsor for safety or behavioral reasons, or the inability of the subject to comply with the protocol required schedule of study visits or procedures at a given study site, with the exception noted in [Section 6.5.3](#). In such circumstances, subjects should be encouraged to remain in contact with the investigator, and to be followed as ODIS subjects, either by attending study visits or via phone visit throughout the remainder of the study in order to provide safety information as it occurs.

If the subject withdraws from the study, and also withdraws consent for disclosure of future information, no further evaluations should be performed, and no additional data should be collected. The sponsor may retain and continue to use any data collected before such withdrawal of consent.

### **6.5.2. Lost to Follow-Up**

Lost to follow-up is defined by the inability to reach the subject by the end of the study only. No subject should be considered lost to follow-up, until the study has been completed. If a subject does not return for a scheduled visit, every effort should be made to contact the subject. Attempts to reschedule the visit should be completed by phone, e-mail, text message, and if necessary, by letter and/or certified mail, in instances where the subject is not responsive to contact attempts. This includes follow-up with persons authorized by the subject as noted above. The study retention team must be contacted, through the retention hotline or delegate, to discuss strategies available for assistance with locating subjects who are potentially lost to follow-up. All efforts to retain a subject, should continue throughout the course of the study and should be documented in the subject's medical source records. Every effort should be made to have the subject complete an EDC or EOS visit and to document subject's vital status, if possible.

If it is determined that the subject has died, the site will use permissible local methods to obtain the date and cause of death. If investigator's use of third-party representative to assist in the follow-up portion of the study has been included in the subject's informed consent, then the investigator may use a Sponsor retained third-party representative to assist site staff with obtaining subject's contact information or other public vital status data necessary to complete the follow-up portion of the study. The site staff and representative will consult publicly available sources, such as public health registries and databases, in order to obtain updated contact information. If after all attempts, the subject remains lost to follow-up, then

the last known alive date as determined by the investigator should be reported and documented in the subject's medical records.

### **6.5.3. Individual Subject Dosing Stopping Criteria**

No subjects will be withdrawn from the study because of lack of compliance with IP administration ([Section 5.3](#)).

During the double-blind, active treatment phase subjects will have clinic visits at regular intervals. The following individual dosing stopping criteria will be followed:

- Dosing with blinded IP (bococizumab, matching placebo) may be temporarily discontinued or stopped for intolerable adverse events, or if the Investigator believes that continuing dosing will be detrimental to the subject's mental or physical health;
- Dosing with blinded IP should be stopped if the subject starts taking a marketed PCSK9 inhibitor;
- Subjects with CK values  $>5 \times$  ULN confirmed by repeat test (Refer to [Section 7.2.5](#)), for whom the CK elevation is associated with muscle pain, muscle tenderness and/or muscle weakness, or new onset renal dysfunction, must be discontinued from study treatment and asked to complete the remainder of the scheduled visits without receiving blinded IP (bococizumab or placebo).

## **7. ASSESSMENTS**

Every effort should be made to ensure that the protocol required tests and procedures are completed as described. However it is anticipated that from time to time there may be circumstances, outside of the control of the investigator, which may make it unfeasible to perform the test. In these cases the investigator will take all steps necessary to ensure the safety and well-being of the subject. When a protocol required test cannot be performed, the investigator will document the reason for this and any corrective and preventive actions which he/she has taken to ensure that normal processes are adhered to as soon as possible. The study team will be informed of these incidents in a timely fashion.

In order to completely and accurately assess the primary and secondary clinical efficacy endpoints and the safety profile of the treatment groups, the vital status of each randomized subject must be obtained at the completion of the study. The occurrence of potential clinical outcome events as defined in [Section 2.2](#) will trigger the compilation of a dossier that includes anonymized supporting medical record information that will be sent to the clinical Adjudication Committee.

### **7.1. Efficacy Assessments**

#### **7.1.1. Clinical Endpoints**

Clinical endpoints defined as primary or secondary efficacy parameters will be assessed beginning with the day of randomization. Cardiovascular adverse events occurring between pre-screening (the time of pre-screening informed consent) and randomization should be

reported as adverse events and not submitted for adjudication. All potential disease-related efficacy endpoints occurring after randomization, through study completion/end of study visit, should be reported as adverse events and submitted for adjudication, whether or not the subject is on double-blind IP. A complete description of these endpoints, their definition, the documentation that needs to be provided for review, and the processes whereby the documentation is prepared and transmitted for adjudication by the Adjudication Committee are detailed in a separate Adjudication Committee Charter. Potential endpoint documentation should include, but is not limited to, any of the following: hospital discharge summaries, operative reports, clinic notes, ECGs, diagnostic test data and/or results, autopsy reports and death certificate information.

The identification of a potential clinical endpoint will be made by the study site and communicated to Pfizer or designated representative immediately (within 24 hours).

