#### **8.14.1. Serious Adverse Event Reporting Requirements**

All SAEs will be reported on the AE eCRF (marked as serious) and on the Clinical Trial SAE report form (available in Firecrest) to be submitted to the Pfizer SAE Triage Group, within 24 hours of investigator's awareness. The form must be completed fully, including an assessment of SAE causality on the submitted forms (see [Section 8.9](#)). The Pfizer SAE Triage Group will identify potential disease-related efficacy endpoint SAEs as defined in [Section 8.6.1](#). The identified potential disease-related efficacy endpoints will not be reported into the Pfizer DSU unless the investigator believes there is a causal relationship between study drug and a potential disease-related efficacy endpoint. Other SAEs that are not potential disease-related efficacy endpoints will be reported to the DSU, by the Pfizer SAE Triage Group.

In particular, if the SAE is fatal or life-threatening, notification to the Pfizer SAE Triage Group must be made immediately, irrespective of the extent of available AE information. This time frame also applies to additional new information (follow-up) on previously forwarded SAE reports as well as to the initial and follow-up reporting of exposure during pregnancy, exposure via breastfeeding and occupational exposure cases.

If a potential disease-related efficacy endpoint SAE is subsequently adjudicated not to be an endpoint, the site will be contacted by the Adjudication Committee and asked to submit an updated SAE form. The form should be revised to show the awareness date (the date of notification by the Adjudication Committee). This form should be submitted to the Pfizer SAE Triage Group within 24 hours of the notification from the Adjudication Committee. This process is shown in [Appendix 9](#).

SAEs must be reported for all subjects (including screen failures) from the time of signing informed consent up to and including 40 days after discontinuing study drug, with this period, including events occurring between pre-screening (the time of pre-screening informed consent) and randomization.

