The PHQ-2 consists of the first two items of the PHQ-9, and constitutes the two core DSM-IV items for major depressive disorder. The PHQ-2 score ranges from 0 to 6. The operating characteristics of this ultra-brief measure are quite good; the recommended cut-point when used as a screening test is a score of 3 or greater. This study will use a screening test score of 2 or greater, as a trigger for completion of the PHQ-9 assessment, as a more conservative approach to identifying the presence of a major depressive disorder. The PHQ-2 provides depressive scores and can be used as a screening assessment for depression; the remaining 7 questions of the PHQ-9 evaluate the severity of depression. The severity is calculated by assigning scores of 0, 1, 2, and 3, to the response categories of “not at all”, “several days”, “more than half the days”, and “nearly every day”, respectively. PHQ-9 total score ranges from 0 to 27. Scores of 1-4, 5-9, 10-14, 15-19, and 20-27 represent minimal, mild, moderate, moderately severe, and severe depression, respectively.

The PHQ-2 will be performed in all subjects at Visit 5 (randomization), and in subjects with cognitive assessments only, it will be performed annually, and at EDC or EOS.

Baseline value will be the last non-missing value on or before the day of randomization.

Adverse events

The Pfizer SAE Triage Group will identify potential disease-related efficacy endpoints (listed below) that are considered by the investigator to be causally related to study drug and report these into the Pfizer Drug Safety Unit (DSU):

- *Myocardial infarction, fatal or non-fatal.*
- *CV death.*
- *All-cause death.*
- *Hospitalization for unstable angina needing urgent revascularization (PCI or CABG).*
- *Stroke, fatal or non-fatal.*
- *Hospitalization for unstable angina.*
- *Hospitalization for congestive heart failure.*
- *Arterial revascularization of any kind (eg, PCI, CABG, peripheral vascular surgery, carotid artery surgery).*

All adverse events occurring on or after the day of first informed consent will be included in reporting, regardless of whether or not the subject is on double-blind study medication. Adverse events during the screening period and adverse events with onset after the first dose of study medication will be summarized separately.

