- Fatal MI;
- Non-fatal MI;
- Any stroke (fatal and non-fatal);
- Any stroke (fatal and non-fatal) of any etiology;
- Fatal stroke;
- Non-fatal stroke;
- Hospitalization for unstable angina;
- Hospitalization for congestive heart failure (CHF);
- Any coronary revascularization procedure;
- CABG;

- PCI;
- Any arterial revascularizations;
- All-cause death.

Adjudicated and confirmed causes of all-cause death will be tabulated by treatment group in the FAS. The tabulation will include the event rates and 95% confidence intervals. Causes of all-cause death will be classified according to the Adjudication Committee Charter.

The number and percent of the component that occurs first for the key secondary composite endpoints of cardiovascular death, non-fatal MI or non-fatal stroke will be summarized by treatment group.

Investigator reported potential secondary endpoint events will be listed.

Circulating biomarker secondary endpoints

Percent changes from baseline in all lipid endpoints and hs-CRP and nominal changes from baseline in LDL-C will be analyzed using a mixed model repeated measures (MMRM) model with fixed effects for treatment (categorical variable), scheduled visit time point (categorical variable), baseline value (continuous variable), interaction between baseline value and scheduled visit time point, interaction between treatment and scheduled visit time point, and geographic region (categorical variable), and complete statin intolerance (categorical variable). Observations will be assigned to visits using the analysis windows in [Table 3](#).

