8.2.3. Analysis of Safety Data

Safety will be assessed through adverse events (including Type 1 and 3 hypersensitivity reactions and injection site adverse events), serious adverse events, vital signs, examination results (physical and neurologic examinations and cognitive testing), 12-lead ECG recordings, and safety laboratory tests including hematology, blood chemistry studies (including liver function tests and creatine kinase tests), urinalysis studies, and ADA assessments. The Safety Analysis Set (SAS) includes all subjects who have received at least one dose of randomized study medication and will be used for all safety analyses, unless otherwise specified. All summaries of safety data will be descriptive only, unless indicated otherwise.

For summaries by visit, observations will be assigned to visits according to the analysis windows in [Table 4](#).

Adverse Events

The Medical Dictionary for Regulatory Activities (MedDRA) will be used to classify all AEs with respect to system organ class and preferred term. AEs, AEs leading to discontinuation from treatment, and SAEs after the first dose of study medication will be tabulated by treatment group. AEs after the first dose of study medication will be summarized without any requirement that the intensity increase after the first dose of study medication. Summaries will also be provided by severity. Summaries by the relationship to study therapy will be presented for AEs and SAEs only.

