In addition, a 3-tier approach will be used. Tier 1 AEs are AEs of special clinical interest, including (but not limited to) Type 1 and Type 3 hypersensitivity reactions and injection site adverse events, and will be specified in the Safety Review Plan. For these events, the number and percentage of subjects with AEs with onset after the first dose of study medication, the risk difference versus placebo, the associated 95% confidence interval, and p-value will be reported. An exact method based on inverting two one-sided tests at half the significance level each (Chan and Zhang, 1999) will be used. The confidence intervals and p-values are not adjusted for multiplicity and are provided for screening purposes only. Tier 2 AEs are those that are not Tier 1, but are common, occurring in $\geq 5\%$ of subjects in any treatment arm. For these events, the number and percentage of subjects with AEs with onset after the first dose of study medication, the risk difference versus placebo and the associated 95% confidence interval will be reported. For these events, the asymptotic method of Miettinen and Nurminen (1985) will be used. The confidence intervals are for estimation purposes only. All events are Tier 3 events and will be summarized as described above.

It should be recognized that this study is not designed to reliably demonstrate a causal relationship between the use of a pharmaceutical product and an adverse event or a group of adverse events. Adverse events in this study are generally not formally adjudicated procedures for the purpose of event classification. Safety analyses are generally considered as exploratory analyses intended to generate hypotheses for further investigation. The 3-tier approach is such an exploratory analysis.

AEs with onset after the first dose of study medication will be tabulated for subjects in subgroups identified in [Section 5.4.2.2](#).

The number and percent of investigator-reported new diagnoses of diabetes with onset after the day of the first dose of study medication will be tabulated by treatment arm in subjects without a baseline history of diabetes.

Injection site adverse events with onset after the day of the first dose of study medication will also be summarized for the bococizumab subjects according to ADA and nAb status.

Vital signs

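### Aggregate SAE and severe-AE rows mix confirmed cardiovascular endpoints with other serious events, and the SAP plans no summary without them

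*Protocol*

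**What the plan says.** Protocol 7.1.1 and SAP 6.1 both require potential disease-related efficacy endpoints to be handled as AEs; they "should be reported as adverse events and submitted for adjudication, whether or not the subject is on double-blind IP". Protocol 8.14.1 puts every SAE on the AE page of the eCRF, with no exception for endpoints. SAP 6.2 sets the scope of reporting: "All adverse events occurring on or after the day of first informed consent will be included in reporting". SAP 8.2.3 sets the tables: "AEs, AEs leading to discontinuation from treatment, and SAEs after the first dose of study medication will be tabulated by treatment group". It adds summaries by severity, and by relationship to study therapy for AEs and SAEs.

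The sponsor separates endpoint events for one purpose only, expedited reporting. Protocol 8.14.1 states: "The identified potential disease-related efficacy endpoints will not be reported into the Pfizer DSU unless the investigator believes there is a causal relationship". The SAP does not carry that separation into the safety analysis.

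The tables are not only totals. MedDRA "will be used to classify all AEs with respect to system organ class and preferred term". For each Tier 1 event, "the risk difference versus placebo, the associated 95% confidence interval, and p-value will be reported". Tier 2 covers preferred terms reaching 5% in an arm and gives a risk difference with interval. Everything else is Tier 3 and is summarized descriptively. Under SAP 8.2.2, "Adjudicated and confirmed causes of all-cause death will be tabulated by treatment group in the FAS", with event rates and confidence intervals.

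**The concern.** The trial is built to show 25% fewer major cardiovascular events. Those events enter the AE and SAE tables next to every other serious event. A row that counts subjects with any SAE therefore adds the hypothesised benefit to whatever harm exists, and the two can cancel.

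This matters most for a diffuse harm. An excess spread over many non-cardiac terms, each below 5%, gets no interval estimate under the tier scheme. It would show mainly in the aggregate row, which is the row where the benefit is mixed in. The trial could then report similar SAE percentages in the two arms while non-endpoint SAEs were moderately raised on bococizumab.

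**Working it through.** **Inputs.** From Protocol 9.1: hazard ratio 0.75, two-sided alpha 0.05, 90% power, 508 events, 5,500 subjects per arm, 2.7%/year on placebo. From Protocol Table 6: 3.8%/year for any CV event at a baseline LDL-C of 100 mg/dL; 2.7 is the lower bound of its 80% prediction interval. Assumed, because the documents give none: placebo non-endpoint SAE rates of 8, 10 and 15%/year.

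**1. The plan's own figure.** Schoenfeld: 4 × (1.960 + 1.282)² / (ln 0.75)² = 508. The required event count is reproduced.

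**2. Break-even excess.** The benefit removes e × (1 − 0.75) from the bococizumab SAE rate, where e is the placebo endpoint rate: 0.027 × 0.25 = 0.675 and 0.038 × 0.25 = 0.95 per 100 patient-years. Dividing by the placebo non-endpoint rate n gives the relative excess that leaves the total SAE rate equal in the two arms.

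| n (%/year, assumed) | e = 2.7%/year | e = 3.8%/year |
|---|---|---|
| 8 | 8.4% | 11.9% |
| 10 | 6.75% | 9.5% |
| 15 | 4.5% | 6.3% |

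These are ratios of rates, so length of follow-up does not enter.

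**3. What the rows would show, at the design rate.** Mean follow-up at 508 events is 508 / (11,000 × (0.027 + 0.02025)/2) = 1.955 years. Take n = 10%/year and the break-even excess of 6.75%.
- Any SAE: total rate 0.10 + 0.027 = 0.127 on placebo and 0.10675 + 0.02025 = 0.127 on bococizumab. Both arms show 1 − exp(−0.127 × 1.955) = 22.0%.
- Non-endpoint SAEs only: 1 − exp(−0.10 × 1.955) = 17.8% against 1 − exp(−0.10675 × 1.955) = 18.8%. The difference is 1.08 points, 95% CI about −0.4 to 2.5, z = 1.46.

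At 8 and 15%/year the corresponding z values are 1.65 and 1.17.

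**4. Cross-check from event counts, primary endpoint only.** Splitting 508 events over 5,500 per arm with S(bococizumab) = S(placebo)^0.75 gives about 289 against 219, a gap of 71 subjects or 1.29 points. If endpoint and other SAEs are independent within an arm, the excess of other SAEs that makes the any-SAE proportions equal is:

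| Placebo non-endpoint SAEs, cumulative (assumed) | Excess, points | Subjects per 5,500 | z without endpoints |
|---|---|---|---|
| 2% | 1.32 | 72 | 4.3 |
| 10% | 1.21 | 66 | 2.1 |
| 20% | 1.07 | 59 | 1.4 |
| 30% | 0.94 | 52 | 1.1 |

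At half or double the endpoint incidence the maskable excess is about 0.5 to 0.7 or 1.9 to 2.7 points. Steps 3 and 4 agree where they overlap: near 18 to 20% cumulative, about 1.1 points and z about 1.4.

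**The case against.** The strongest reply is that the plan already separates the two kinds of event in most places that matter. Clinical endpoints have their own adjudicated time-to-event analyses. Causes of death are adjudicated and tabulated with rates and intervals. Hemorrhagic stroke is also reported as a safety endpoint. Organ-class, preferred-term and tier rows without endpoint terms cannot be offset. The DMC reviews unblinded safety data, with a flag for harm on all-cause death. Safety summaries are descriptive, and risk differences are specified for Tier 1 and Tier 2 events, not for an any-SAE total. Such a total correctly counts all SAEs; it simply answers a different question. All of this stands and limits the point to aggregate rows.

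Two further limits stand. Protocol 8.7 says that procedures are not AEs, only the condition that led to them, so revascularizations enter only through that condition. Protocol Section 3 expects subjects with a clinical event to stay on treatment, so AEs leading to discontinuation should be little affected.

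On size, 3.8%/year is for any CV event including coronary revascularization, while the design uses 2.7; hence a range. The protocol does not assume 0.75 for every endpoint type, such as heart-failure hospitalization. At the lower rate the masked excess would usually not reach significance in the added table either (step 3). That is true, but the table's purpose is an estimate with an interval.

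None of this supplies a summary of serious events without the confirmed endpoints.

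**Conclusion.** The point holds in a limited form and supports an inexpensive addition. Aggregate SAE and severe-AE rows, and organ-class totals containing MI or stroke, can offset a diffuse excess of other serious events. The offset is 0.675 to 0.95 per 100 patient-years, equal to the relative excesses in step 2.

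This rests on a real cardiovascular benefit at a hazard ratio of 0.75, on assumed non-endpoint SAE rates, and on the SAE tables being drawn from the eCRF. The SAP does not name the source; a drug-safety source would omit endpoint events not judged drug-related. The figures in steps 3 and 4 also assume 508 events. The program stopped on 01 November 2016 and the documents do not say how many had accrued.

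A reader might infer that a cardiovascular benefit would hide an excess of other serious events throughout the safety report. The documents do not support that. Harm concentrated in particular non-endpoint terms remains visible by organ class, preferred term or tier, and non-cardiovascular deaths remain visible by adjudicated cause. Masking also needs both a benefit and an excess of similar size.

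**What to change.** In SAP 8.2.3, keep the all-inclusive tables and state that they include endpoint events and which database they use. Add supportive overall SAE and severe-AE summaries by arm, with risk difference and 95% CI, that exclude events adjudicated and confirmed as cardiovascular efficacy endpoints: CV death, MI, stroke of ischemic or undetermined etiology, hospitalization for unstable angina or heart failure, and the conditions underlying confirmed revascularizations.

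Retain non-cardiovascular deaths, hemorrhagic stroke and events adjudicated as not an endpoint. The list in Protocol 8.6.1 should not serve as the exclusion list, because it contains all-cause death and would remove possible harm. Because SAP 6.1 sends only events up to 01 November 2016 for adjudication, the SAP should also say how later, unadjudicated events are treated in these summaries.

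The cost is a few more safety tables and a merge of AE records with adjudication results already held. Data collection and conduct do not change. The drawback is that classification depends on post-randomization adjudication, so the new summaries should remain supportive.
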